### **8.3. Subject Withdrawal Criteria**

#### **8.3.1. Procedures for Discontinuation or Withdrawal of a Subject**

##### **8.3.1.1. Discontinuation of Trial Treatment**

Discontinuation of trial product can be decided by either the investigator or the subject. A participant may discontinue his or her participation without giving a reason at any time during the trial.

Participants who discontinue trial product should continue with the scheduled visits and assessments to ensure continued counselling and data collection.

If the subject does not wish to attend the scheduled clinic visits, efforts should be made to have the visits converted to phone contacts. However, all efforts should be made to have the subject attend at least the 'end of treatment' clinic visit containing the final data collection of primary and confirmatory secondary efficacy endpoints, and the 'end of trial' visit.

The 'end of trial' visit is scheduled approximately 2 weeks after the final data collection, to ensure the safety of the subject. If the subject has discontinued trial product >2 weeks prior to the 'end of treatment' visit, and the requirements for the follow-up period prior to the 'end of trial' visit is fulfilled, then the 'end of trial' visit can be performed in combination with 'end of treatment' visit.

If the subject refuses to attend the 'end of treatment' and/or 'end of trial' visit, information about the attempts to follow up with the subject must be documented in the subject's medical record.

The subject must be discontinued from trial product if any of the following applies:

1. Safety concern as judged by the investigator
2. Pregnancy
3. Intention of becoming pregnant
4. Liver function test (LFT) abnormalities meeting specified discontinuation criteria (refer to [Appendix A](#) for discontinuation criteria and instruction on management of LFT abnormalities)
5. Confirmed pancreatitis (see below)

If acute pancreatitis is suspected based on clinical signs and symptoms, blinded study medication should be interrupted immediately, and appropriate diagnostic assessments should be performed.

- A diagnosis of acute pancreatitis requires at least 2 of the following 3 findings :
  - abdominal pain consistent with acute pancreatitis (persistent, severe epigastric pain, frequently radiating to the back); abdominal pain is often associated with nausea and vomiting.
  - serum lipase and/or amylase activity  $\geq 3X$  the laboratory ULN
  - characteristic findings of acute pancreatitis on imaging

- If a diagnosis of pancreatitis is confirmed, the subject will be discontinued from blinded K-757/placebo and appropriate treatment and monitoring must be initiated.
- If the investigator and Sponsor agree that acute pancreatitis has been ruled out, all investigational medicinal products (IMP) should be resumed.

The primary reason for discontinuation of trial product must be specified in the source data at the time of discontinuation, and the subject should continue to follow the visit and assessment schedule. The reasons for treatment discontinuations are:

- Adverse event
- Withdrawal of consent
- Lost to follow up
- Pregnancy/Intention to become pregnant
- Death
- Investigator decision
- Significant protocol deviation

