Observational data have suggested the possibility that agents enhancing Glucagon-like peptide-1 receptor (GLP-1R) mediated pharmacology, including GLP-1R agonists and DPP-4is, may increase the risk of acute pancreatitis, though statistically significant effects have not been identified in large cardiovascular outcomes trials (CVOTs) conducted with these agents. A recent metaanalysis of CVOT data did identify a 75% risk increase of acute pancreatitis with DPP-4is, though found no effect of GLP-1R agonists. No preclinical or clinical data generated to date have suggested that K-757 may increase the risk of pancreatitis. However, given the early stage of K-757 development, individuals with any history of acute or chronic pancreatitis are excluded from this study, as are those with excessively elevated amylase and/or lipase at screening. Markedly elevated fasting triglycerides are also exclusionary given the potential for hypertriglyceridemia to precipitate pancreatitis. Though GLP-1R agonists and DPP-4 is are commonly associated with increases in serum amylase and lipase activity, such isolated biochemical changes in the absence of suggestive signs/symptoms have not been predictive of pancreatitis. Serum lipase will be assessed at specified junctures during treatment (see Table 2). Note that protocol criteria for interrupting and discontinuing study medication for suspicion of acute pancreatitis require symptoms and/or imaging consistent with pancreatitis (see Section 8.3).

Review to Section 10.1 for discussion of prohibited and allowed concomitant medications.

Full inclusion and exclusion criteria are provided in Section 8.1 and Section 8.2, respectively.

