### 13. STUDY DRUG MATERIALS AND MANAGEMENT

#### 13.1. Study Drug

In this protocol, the term study medication refers to all or any of the drugs defined below and in Table 11 and Table 12.

Details regarding the dosage form description and strengths of the active drug and placebo can be found in the Pharmacy Manual or equivalent manual. Study drug will be packaged to support enrollment and replacement of participants as required.

The study site will be supplied to the study site / Investigator by the Sponsor with the following medication in a double-blind manner:

- K-757 30-mg and 60-mg capsules and placebo capsules. Capsules will be provided in polyvinyl chloride (PVC)/polyvinylidene chloride (PvDC) blisters with aluminum base as a primary package. Blister strips are then secondary packaged into wallet cards to meet the required dosing regimen. Participants are blinded as to the study treatment they receive.
- K-833 100-mg capsules and placebo capsules. Capsules will be provided in PVC/PvDC blisters with aluminum base as a primary package. Blister strips are then secondary packaged into wallet cards to meet the required dosing regimen. Participants are blinded as to the study treatment they receive.

Blister packs will be labeled with a single-panel label that will contain, but will not be limited to, the following: Sponsor's name and address, protocol number, packaging job/lot number, caution statement and storage conditions.

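### The confirmed-pancreatitis instruction in Protocol 8.3.1.1 stops only K-757/placebo, although the rule it carries out requires stopping trial product as a whole

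*Protocol*

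**What the plan says.** Protocol Section 8.3.1.1 introduces its list of mandatory stops with "The subject must be discontinued from trial product if any of the following applies". Item 5 on that list is confirmed pancreatitis, with a pointer to the text below.

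That text has three steps:

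- **Suspected on signs and symptoms:** "blinded study medication should be interrupted immediately, and appropriate diagnostic assessments should be performed".
- **Confirmed:** "the subject will be discontinued from blinded K-757/placebo and appropriate treatment and monitoring must be initiated".
- **Ruled out, with investigator and sponsor in agreement:** "all investigational medicinal products (IMP) should be resumed".

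Section 13.1 lists two products. One is K-757 in 30 mg and 60 mg strengths with placebo; the other is "K-833 100-mg capsules and placebo capsules". It also states that "the term study medication refers to all or any of the drugs defined below" and in Tables 11 and 12, which cover K-757 and K-833 respectively.

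**The concern.** Item 5 does not set out the action itself but sends the reader to the bullets, so the confirmed-case bullet is where a site will look for what to do. That bullet mentions one product. The bullet after it refers to all investigational products, so a careful reader could take the narrower wording as deliberate.

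Read literally, K-833 or its placebo would have been interrupted on suspicion but left outside the permanent stop. Section 13.4.3 leaves resumption after an interruption of 7 or more consecutive days, whatever the cause, to discussion between the PI and the Sponsor Clinical Director. A component regarded as merely interrupted could appear to fall under that discretionary rule. Item 5 should prevent this, but a site should not have to reconcile several sections to apply a mandatory safety stop.

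**Working it through.** The plan states no figure on this point, so the check compares scope across the text and then counts who could be affected.

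**Scope of each statement**

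| Place in the Protocol | Step | Scope |
|---|---|---|
| 8.3.1.1, list header and item 5 | Mandatory stop | Trial product, not limited to one component |
| 8.3.1.1, suspicion | Interrupt | Blinded study medication |
| 8.3.1.1, confirmed | Discontinue | K-757/placebo only |
| 8.3.1.1, ruled out | Resume | All investigational products |
| 5.5, description of the Section 8.3 criteria | Interrupt and discontinue | Study medication |

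Only the confirmed-case bullet is limited to one product. The Section 5.5 description matters because it covers discontinuation as well as interruption and does not confine the criteria to K-757.

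**Is there a stated reason to exempt K-833?** None in the readable text. The pancreatitis rationale in Section 5.5 names only K-757 ("No preclinical or clinical data generated to date have suggested that K-757 may increase the risk of pancreatitis"), which may explain how the wording arose. That rationale starts, however, from agents that enhance GLP-1 receptor pharmacology, and Section 5.1 predicts greater hormone secretion from GPR40 and GPR119 co-agonism than from a single agent. Section 5.3 confirms that there is no K-833-only arm, so K-833 alone is not a regimen under study. Much of the prior-experience text is redacted, so nothing can be inferred from its silence.

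**Who could be affected**

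- Blinded components per participant (Table 9, Section 13.1): K-757/placebo and K-833/placebo = 2. Named in the bullet: 1 of 2.
- Participants taking a K-833 or matching placebo capsule (Table 9, Section 7.2): 50 + 50 + 50 = 150.
- Participants on active K-833: combination 50, K-757 alone 0, placebo 0. Share: 50/150 = 33.3%.
- Participants whose K-833 capsule is placebo: 100/150 = 66.7%.

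The 33.3% follows from the 1:1:1 allocation. It shows where a literal reading could leave active drug unaddressed; it is not a risk estimate. The documents give no pancreatitis rate. Few cases are expected, because entry excludes any history of pancreatitis (criterion 20), amylase or lipase above 1.2 times ULN (criterion 30) and triglycerides above 600 mg/dL (criterion 31).

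**The case against.** The strongest reply is that the protocol already closes the gap. The binding instruction is the list header with item 5, and it covers trial product. The bullet never says only, so naming one component does not contradict stopping both. By the time of confirmation everything has been interrupted, and the one restart condition stated in Section 8.3.1.1, that pancreatitis has been ruled out, cannot then be met. Item 1 separately requires a stop for any safety concern judged by the investigator, and Section 7.4 allows no dose adjustment. A site would have to restart K-833 uninstructed and against item 5.

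Most of this stands. It makes continued K-833 dosing after a confirmed case unlikely, and it means the bullet is incomplete rather than an order to keep dosing. It does not remove the mismatch: the bullet that item 5 points to is still narrower than item 5. The Section 5.5 description, sometimes the best support for a whole-regimen reading, also confirms that this bullet is the exception.

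**Conclusion.** The point holds and is minor. The confirmed-pancreatitis bullet names 1 of the 2 blinded components, while the rule it implements covers trial product. The consequence is confined to a literal reading of the bullet, and active drug is at issue only for a confirmed case in the combination arm (50 of 150). There is no effect on sample size, power, alpha, endpoints or analysis.

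The conclusion assumes that trial product means both drugs and their placebos. The protocol does not define that term separately, but the neighbouring steps and Section 13.1 support this reading. It also assumes that no redacted passage sets out a deliberate exemption for K-833; even if one did, the bullet and item 5 would still need to be reconciled.

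**What to change.** In the confirmed-pancreatitis bullet of Section 8.3.1.1, replace the reference to blinded K-757/placebo with: all blinded study medication (K-757, K-833 and matching placebos). The components should be spelled out because the Section 13.1 definition allows study medication to mean any one of the drugs as well as all of them.

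The cost is one phrase in a protocol amendment or clarification letter, with no added visits, procedures or participants.

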#### **8.3.1.2. Early Withdrawal from the Trial**

Early withdrawal from the trial may occur due to voluntary withdrawal of consent, lost to follow up (see below), or death.

In all other cases of trial product discontinuation, participants should be followed as described above in Section [8.3.1.1](#).

If a subject ends his/her participation, the investigator must ask the subject if he/she is willing, as soon as possible, to have assessment performed according to the 'end of treatment' visit.

Final drug accountability must be performed even if the subject is not able to come to the trial site.

Although a subject is not obliged to give his/her reason(s) for withdrawing early, the investigator must make a reasonable effort to ascertain the reason(s), while fully respecting the subject's rights. Where the reasons are obtained, the primary reason for withdrawal must be specified in the end of trial form in the case report forms (CRF).

#### **8.3.1.3. Lost to Follow-up**

A subject will be considered lost to follow-up if he or she repeatedly fails to return for scheduled visits and is unable to be contacted by the trial site.

The following actions must be taken if a subject fails to return to the trial site for a required visit:

- The site must attempt to contact the subject and reschedule the missed visit as soon as possible and counsel the subject on the importance of maintaining the assigned visit schedule and ascertain whether the subject wishes to and/or should continue in the trial.

- Before a subject is deemed lost to follow-up, the investigator must make every effort to regain contact with the subject (where possible, at least three telephone calls and, if necessary, a certified letter to the subject's last known mailing address or local equivalent methods). These contact attempts should be documented in the subject's source document. Should the subject continue to be unreachable at the 'end of treatment' visit, he/she will be considered to have withdrawn from the trial with a primary reason of lost to 'follow-up'.

## 9. STUDY SCHEDULE AND STUDY PROCEDURES

The order of priority can be changed during the study with joint agreement of the Investigator and KALLYOPE, Inc.

Any nonscheduled procedures required for urgent evaluation of safety concerns take precedence over all routine scheduled procedures.

- Adherence to the trial design requirements, including those specified in the flowchart, is essential and required for trial conduct.
- Assessments should be carried out according to the clinic's standard of practice unless otherwise specified in the current section. Efforts should be made to limit the bias between assessments. The suggested order of the assessments:
  - Electrocardiogram (ECGs) and vital signs (including body weight when assessed)
  - Blood samples
  - Mental health assessment instrument
  - Other assessments
- Source data of clinical assessments performed and recorded in the CRF must be available and will usually be the subject's medical records. Additional recording to be considered source data includes, but is not limited to laboratory reports, ECG and Mental Health assessments.
- Subject's weight history must be recorded in the subject's medical record.
- Review of mental health assessment instruments, ECG and laboratory reports must be documented either on the documents or in the subject's source documents.
  - Repeat laboratory samples may be taken for technical issues.
  - Efficacy assessments and procedures are described in [Section 14](#)
  - Safety assessments and procedures are described in [Section 15](#)
  - Procedures related to AE evaluation and reporting are in [Section 15.2](#)
  - Procedures around study drug admin are in [Section 13](#)

### 9.1. Prestudy (Screening) Procedures

Informed consent must be obtained before any trial related activity.

At screening the investigator should ascertain whether there may be important barriers to participant motivation for lifestyle change and compliance with the protocol (e.g. density and timing of study visits). The interview must be conducted at screening to assist in identifying subjects who are unable or unwilling to comply with protocol procedures as per the exclusion criteria. In addition, the interview will ensure that any minor barriers are addressed during lifestyle counselling.

Within 4 weeks of Randomization, potential participants will be evaluated to determine that they fulfill the entry requirements as set forth in the Inclusion and Exclusion Criteria. The Investigator will discuss with each subject the nature of the study, its requirements, and its restrictions.

The pre-study screening assessments (V1) are detailed in the SOA. Subjects need not be fasted for this visit.

- All screening evaluations must be completed and reviewed to confirm that potential subjects meet all eligibility criteria.
- The investigator will maintain a screening log to record details of all subjects screened and to confirm eligibility or record reason for screen failure, as applicable.
- At screening, subjects will be provided with a card stating that they are participating in a trial and giving contact details of relevant trial site staff.
- For details on the procedures, please refer to [Table 2](#) and Section [15](#).

## **9.2. Procedures Weeks 1 through 13 (Treatment Period)**

Participants will return to the clinical research unit at various Weeks/Visits until completion of the Visit 12 post-dose procedures (Day 92). The specific procedures that will be performed during this timeframe and at each visit are detailed in [Table 2](#). Details related to timing of specific procedures relative to meals and dosing are in Section [15](#).

Visits 2 through 12 will be performed during the Treatment Period. Two of these visits (V7 (Day 36) and V11 (Day 85)) are phone call only visits with the others requiring a clinic visit. At these visits, the clinical research unit will conduct a telephone call to all participants to determine if any new AEs have arisen or concomitant medications have been taken. Study drug compliance will also be checked.

### Mandatory fasted visits:

Amongst the in-person clinic visits during the Treatment Period, V2 (randomization), V6 (Day 29), V9 (Day 57) and V12 (Day 92), subjects should come to the clinic in the fasted state because body weight and fasting lipids need to be assessed in the fasted state. These fasted visits should be scheduled in the morning and the AM dose of study medication should be taken after collection of blood. Dosing should be witnessed at these visits. Other in-person visits during the Treatment Period can be in the fasted or fed state and may be scheduled without regard to timing of study medication.

## **9.3. Poststudy Procedures**

Participants will return to the clinical research unit for the Poststudy procedures at V13. Participants should fast prior to this visit and arrive at the clinic in the fasted state. The specific assessments to be performed are list in the SOA ([Table 2](#)).

## 10. STUDY RESTRICTIONS

### 10.1. Prior and Concomitant Medications

Participants should be instructed not to start any new medications (prescription or non-prescription) or supplements without first consulting with the investigator. If this is not possible due to medical urgency, the participant should inform the investigator as soon as possible.

[figure not shown]
Any medication (including over-the-counter and prescription medicines) other than the trial product, that the participant is taking at the time of screening or receives during the trial must be recorded on the appropriate electronic case report form (eCRF). Information collected will include:

1. Medication name
2. Indication
3. Dates of administration including start and stop dates
4. Dose

Medications or vaccinations specifically prohibited in the exclusion criteria are not allowed during the ongoing trial. If there is a clinical indication for any medication or vaccination specifically prohibited during the trial, discontinuation of study medication may be required. The investigator should discuss any questions regarding this with the Sponsor Clinical Director. The final decision on any supportive therapy or vaccination rests with the investigator and/or the subject's primary physician. However, the decision to continue the subject on trial therapy requires the agreement of the Sponsor.

#### **Prohibited Medications**

Medications listed below are prohibited from screening through the post-study follow-up visit.

- 
2. Corticosteroids: Treatment for  $\geq 14$  consecutive days or repeated courses of pharmacologic doses of corticosteroids. **Note:** Inhaled, nasal, and topical corticosteroids and physiological replacement doses of adrenal steroids are permitted.
  3. Any anti-hyperglycemic medications
  4. Any weight-loss medications: Treatment with or initiation of any weight-loss medication (e.g., semaglutide, liraglutide, orlistat, phentermine, phentermine-topiramate, bupropion-naltrexone) is prohibited. This includes agents that are approved as a

component of a multi-drug combination treatment for obesity, regardless of the purpose of current use, with the exception of bupropion.

Bupropion, which is a component of the naltrexone-bupropion combination approved for weight loss (Contrave™), is also approved as a single agent for the treatment of depression. Bupropion is allowed if it is being used for treatment of depression and eligibility criteria for anti-depressant medication stability prior to screening are met (see Exclusion Criterion #12).

5. Marijuana: Legal (including medicinal marijuana and any marijuana-derived product including THC or CBD) or illegal use is prohibited.
6. Supplements and/or Traditional Medicines: The introduction of new agents during the course of the study is not allowed. The use of prior agents is described below.
7. Lipid-lowering agents other than HMG-CoA reductase inhibitors (statins) and ezetimibe are prohibited. Prohibited agents include:
  - Bile acid binding resins (e.g. cholestyramine, colesevelam)
  - Fibric acid derivatives (e.g. fenofibrate, clofibrate)
8. Anti-psychotic agents are prohibited, regardless of the purpose for their use.
9. Use of the following anti-depressants is prohibited, regardless of the purpose for their use:
  - Tricyclic (e.g. amitriptyline, clomipramine) and tetracyclic (maprotiline) anti-depressants
  - Mirtazapine
10. Stimulant medications including amphetamines (e.g. dextroamphetamine, lisdexamfetamine) and methylphenidate/dexmethylphenidate.
11. Opiates: Brief ( $\leq 2$  total days) use of opiates for unanticipated pain management needs during study participation is permitted. All other use of opiates is prohibited.
12. Use of any other medications that, in the investigator's judgement, can significantly impact (increase or decrease) body weight, regardless of the purpose for their use.

